#### **13.1 Adverse Event Definition**

This study does not have specific adverse events. All the interventions are part of regular surgical care. The device is not in direct contact with the subject during the surgery. Obtaining the gas sample will remove about 500 ml of gas for 90 seconds (1.5 minutes), which is

automatically replaced by the CO2 inflow simultaneous with gas sample collection. Therefore, it is not anticipated the abdominal pressure to decrease below 12 mm/Hg.

### **13.1.1 Investigational Agent or Device Risks (Expected Adverse Events)**

We believe this is a nonsignificant risk device as the device and the expected risk is no more than the minimal risk.

The device:

- Does not come into direct contact with the subject during the surgery
- Does not introduce any energy to the subject

Further, the device will be labeled appropriately and examined by the biomedical engineering at operating rooms at WCMC-NYPH.

### **13.1.2 Adverse Event Characteristics and Related Attributions**

#### **Not Applicable**

*Specify the adverse event reporting system you will utilize for tracking adverse events during the conduct of this study (i.e., NCI Common Terminology Criteria for Adverse Events (CTCAE), Vaccine Adverse Event Reporting System (VAER), Division of AIDS (DAIDS) Table for Grading the Severity of Adult and Pediatric Adverse Events, Manufacturer and User Facility Device Experience Database (MAUDE) and the Special Nutritionals Adverse Event Monitoring System).*

*For example, the following text is text that may be used when utilizing the CTCAE and should be changed to reflect the correct AE reporting system.*

**CTCAE term (AE description) and grade:** The descriptions and grading scales found in the revised NCI Common Terminology Criteria for Adverse Events (CTCAE) version 5.0 will be utilized for AE reporting. A copy of the CTCAE version 5.0 can be downloaded from the CTEP web site (<http://ctep.cancer.gov>).

- **Attribution** of the AE:
  - Definite – The AE *is clearly related* to the study treatment.
  - Probable – The AE *is likely related* to the study treatment.
  - Possible – The AE *may be related* to the study treatment.
  - Unlikely – The AE *is doubtfully related* to the study treatment.
  - Unrelated – The AE *is clearly NOT related* to the study treatment.

### **13.1.3 Recording of Adverse Events**

While this study will not report adverse events related to the study, the study will collect all the intraoperative complications and record them on the data collection forms in the subject's research chart. All complications, should there be any, will be recorded in the subject's medical record as they are part of the regular surgical care.

We do not have expected adverse events related to the Perf-AlertTM device use. However, we are reporting unanticipated problems/ unexpected adverse events, which include if the Perf-AlertTM device stopping work during surgery or malfunction, and these events will be reported to the IRB,

and the device's sponsor Sentire Medical Systems, Inc., USA. This is described in section 14.1.2 of the protocol and is now added to sections 13.1.3 and 13.2.3 of the protocol. In general, we are collecting intraoperative and postoperative complications.

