### 7.1 Study Intervention/Device Description

The Perf-Alert™ device consists of a 15" x 13" x 7" unit containing gas sensors and valves, an ultra-low pressure pump, user controls (buttons), and software algorithms, which control the operation of the device. It is used in conjunction with a single-use, disposable kit consisting of sterile tubing and filters used for sample collection and transport. The sensing unit will be connected via a sterile tube/filter set to any trocar port in use during the procedure. At specific time points during the procedure, a one-way valve will be opened, and the unit's pump turned on is withdrawing small aliquots of gas from the abdominal cavity to the sensing unit. The system's architecture is configured such that sample collection, transport, analysis, and feedback occur in a single step such that sample collection and sensor feedback occur in real-time. A standard laptop running an analytical software program is connected to the unit to record and log sensor readings. The device will sit outside the sterile operative field and operated by a study coordinator with a representative of the device manufacturer present in the operating for troubleshooting.

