## **8. Study Intervention Discontinuation and Participant Discontinuation/Withdrawal**

### **8.1 Discontinuation of Study Intervention**

Any irregularity or complication during the surgery being performed will be grounds for discontinuation of the study intervention and withdrawal of the subject from the study. If the laparoscopic surgery has to be converted to an open surgical approach due to medical reasons or technical reasons, the study intervention will be discontinued and the subject withdrawn from the study.

No data will be collected at the time of study intervention discontinuation, and any data previously collected will be excluded from the study analysis and appropriately destroyed.

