### **8.2 Participant Discontinuation/Withdrawal from the Study**

Participants are free to withdraw from participation in the study at any time upon request. An investigator may discontinue or withdraw a participant from the study for the following reasons:

- If any clinical adverse event (AE), laboratory abnormality, or other medical condition or situation occurs such that continued participation in the study would not be in the best interest of the participant

The reason for participant discontinuation or withdrawal from the study will be recorded on the on the intraoperative Case Report Form (CRF) and reflected in the WCMC subject registration site. Subjects who sign the informed consent form but do not receive the study intervention may be replaced. Subjects who sign the informed consent form, and receive the study intervention, and subsequently withdraw, or are withdrawn or discontinued from the study will be replaced.

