**12.2 Sample Size/Accrual Rate**

As this is a pilot study, a sample of 20 consecutive subject corresponding to the inclusion and exclusion criteria will accrued for the two study cohorts. Cohort 1- 10 subjects and Cohort 2- 10 subjects.

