**12.4 Analysis of Endpoints**

**12.4.1 Analysis of Primary Endpoints**

The gas sample gas composition will be analyzed automatically by the Perf-Alert™ gas detection system at the 8 different predetermined time points listed in 12.1. The measurements will be recorded in the data collection forms. The maximum value for the particular sample gases – H2 and CH4, will be recorded and included in the descriptive analysis.

Specifically, the presence of Hydrogen (H2) and Methane (CH4) gas measured in ppm or mg/L (parts per million or milligrams per liter (mg/L) at the 8 time points during the surgery will be descriptively assessed. Descriptive statistics (e.g., mean, standard deviation, median, interquartile range, frequency and percent) will be calculated for these parameters. Ninety-five percent confidence intervals will be calculated for all parameters of interest to assess the precision of the obtained estimates. No formal hypothesis testing will be performed in the pilot study. However, pairwise time point comparisons will be evaluated by the paired t-test or Wilcoxon signed-rank test, as appropriate. Due to the small sample size in this pilot study, all analyses will be considered exploratory and hypothesis-generating with no adjustment for multiple comparisons. All p-values will be two-sided with statistical significance evaluated at the 0.05 alpha level. All analyses will be

conducted using SPSS for Windows v.25 (IBM Corp. Released 2016. IBM SPSS Statistics for Windows, Version 24.0. Armonk, NY: IBM Corp).

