**13.2.3 Reporting of SAE to Sentire Medical Systems, Inc.**

We are reporting Unanticipated Problems/ Unexpected adverse events which include the Perf-AlertTM device stop working during surgery, or malfunction, and these events will be reported to the IRB and the device sponsor Sentire Medical Systems, Inc., USA. This is described in section 14.1.2 of the protocol, and now added to In general we are collecting intraoperative and postoperative complications.

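### The plan does not say how a device stoppage, malfunction or unusable sample enters the detection result, and sections 8.1 and 8.2 can be read to delete and replace such cases

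*Combined protocol and SAP*

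**What the plan says.** **Aim.** The Protocol Summary and 2.2 describe a study of device performance: connecting to a standard trocar, drawing gas at intervals and detecting bowel content accurately.

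**Device failure.** Section 13.1.3 speaks of unexpected events "which include if the Perf-AlertTM device stopping work during surgery or malfunction", and has these reported to the IRB and the manufacturer. Section 13.2.3 repeats the rule for a device that may "stop working during surgery, or malfunction, and these events will be reported to the IRB and the device sponsor Sentire Medical Systems, Inc., USA". No other consequence is given.

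**Response and analysis.** Section 10.1 counts a measurement of CH4 and/or H2 with the bowel open as a positive response. In 12.4.1, "The maximum value for the particular sample gases" is recorded and summarised, including frequency, percent and 95% confidence intervals. Neither section mentions a failed or missing reading or gives a denominator. Both parts of 12.6 (Reporting and Exclusions) are marked not applicable. The Sample Collection Table in 6.1.2 has no field for the validity of a reading or a repeat attempt.

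**Withdrawal and replacement.** Section 8.1 states: "Any irregularity or complication during the surgery being performed will be grounds for discontinuation of the study intervention and withdrawal of the subject". It adds that readings already taken are left out of the analysis and destroyed. Under 8.2, subjects who received the study intervention and "subsequently withdraw, or are withdrawn or discontinued from the study will be replaced".

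**Completion.** Under 3.4, a subject has completed the study once the laparoscopic colectomy with intracorporeal anastomosis is completed. The device is not part of that test.

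**Support in the room.** Under 7.1 a study coordinator operates the device, "with a representative of the device manufacturer present in the operating for troubleshooting".

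**The concern.** From the user's side, a detector that gives no reading while the bowel is open has missed the gas. The protocol expects that this may happen, but the event goes only into a reporting channel. Nothing carries it into the result that the study exists to produce.

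The handling would then be settled case by case, possibly after readings have been seen. If the subject is replaced or the sample left blank, the detection rate becomes conditional on a working device. If a zero is entered, the miss is counted in the rate, but absence of a reading is mixed with absence of gas in the concentration summaries and the paired comparisons. A reading obtained after a fault has been cleared would look the same as a first-attempt reading.

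Two losses could not be repaired at analysis: data destroyed under 8.1, and a per-sample status that was never collected. Replacement would also weaken the bias safeguard of consecutive enrolment in 7.11 and 12.2 ("a sample of 20 consecutive subject corresponding to the inclusion and exclusion criteria").

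**Working it through.** **The plan's own figure.** Section 12.2 sets 10 + 10 = 20 subjects because this is a pilot. It gives no formula, expected detection rate or precision target, so there is nothing further to reproduce.

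**Inputs.** N = 20 and two cohorts of 10 (12.2); 95% intervals (12.4.1). The number of failures k is an assumption, because the documents give no failure rate. It is also assumed that every other case is positive and that the device gives no reading at any open-bowel sample in a failed case.

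**Formula.** Exact (Clopper-Pearson) limits for x detections out of n: lower = Beta⁻¹(0.025; x, n − x + 1), upper = Beta⁻¹(0.975; x + 1, n − x). When x = n, the lower limit is 0.025^(1/n) and the upper limit is 100%. For example, 0.025^(1/20) = 0.832.

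**Step 1: same failures, different handling.** Under replacement, k further subjects are enrolled, so n rises from 20 to 20 + k once all attempts are counted. With blanks, the reported rate is (20 − k)/(20 − k) and the all-attempts rate is (20 − k)/20.

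| k | Route | Failures left out | All attempts counted |
|---|---|---|---|
| 1 | replaced | 20/20 = 100% (83.2–100) | 20/21 = 95.2% (76.2–99.9) |
| 1 | blank | 19/19 = 100% (82.4–100) | 19/20 = 95.0% (75.1–99.9) |
| 2 | replaced | 20/20 = 100% (83.2–100) | 20/22 = 90.9% (70.8–98.9) |
| 2 | blank | 18/18 = 100% (81.5–100) | 18/20 = 90.0% (68.3–98.8) |
| 4 | replaced | 20/20 = 100% (83.2–100) | 20/24 = 83.3% (62.6–95.3) |
| 4 | blank | 16/16 = 100% (79.4–100) | 16/20 = 80.0% (56.3–94.3) |

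**Step 2: one cohort of 10, one failure.** Replaced: 10/10 (100%, 69.2–100) against 10/11 (90.9%, 58.7–99.8). Blank: 9/9 (100%, 66.4–100) against 9/10 (90.0%, 55.5–99.7).

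**Step 3: entering zero.** With k = 2 and no replacement, the detection rate is 18/20, the same as counting all attempts. The concentration summary changes, however. If the 18 valid readings have mean m, the reported mean is (18 × m + 2 × 0)/20 = 0.9m, which is 10% too low for a reason unrelated to gas.

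**Step 4: how likely is it to matter?** The chance of at least one failure in 20 cases is 1 − (1 − p)^20. For an assumed per-case probability p of 2%, 5%, 10% or 20%, this is 33%, 64%, 88% or 99%.

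**The case against.** **Silence is not a rule.** A reader might infer that malfunction cases never reach the result, that detection will be reported only where the device worked, and that the bias always favours the device. The documents do not support this. No section says that failed samples are left blank or that malfunction cases are replaced, and a failed reading could equally be entered as zero and counted as a miss.

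**Replacement needs a broad reading.** The ground in 8.1 is an irregularity or complication during the surgery, and the investigator's ground in 8.2 is clinical. Neither names the device. Under 3.4, a subject whose device stops but whose operation is completed is a completer. This stands as far as it goes, but irregularity is undefined in 8.1, so the passages leave the question open.

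**The direction can reverse.** A subject with a positive reading at colotomy whose device failed at anastomosis completion would lose a true detection if withdrawn under 8.1. If 18 of 20 were positive, removing one positive gives 17/19 = 89.5% against 90.0%.

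**One failed sample need not cost a subject.** Gas is sampled at more than one point around bowel opening, and under 10.1 a detection of either gas suffices.

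**Failures can be traced.** They are reported to the IRB and manufacturer, the laptop logs sensor readings, and 8.2 has the withdrawal reason recorded on the CRF. That allows some later counting. It does not commit the study to a denominator, and it does not bring back data destroyed under 8.1.

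**This is an exploratory pilot.** Counting failures as misses is not the only valid main analysis, and 12.4.1 names no subject-level detection rate as the main result. Both points are fair, and they are a reason to show two rates side by side. They are not a reason to leave the handling open when a percentage and its interval will be reported.

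**Conclusion.** The concern holds as a gap in the plan. Device failure is foreseen but given no place in the detection result, and 8.1 and 8.2 leave open a route by which such cases could be removed and replaced, in tension with 3.4.

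Under the stated assumptions, each failure left out moves a perfect overall result by about 4 to 5 percentage points, and by 9 to 10 points within a cohort of 10. The size rests on an assumed failure count, on all other cases being positive, and on no open-bowel reading in the failed cases. If no device fails, nothing changes. A systematic bias toward the device has not been shown. What is shown is that the same operations can yield different results, and that the plan does not choose between them.

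The point should be settled before data collection, because the remedy is cheap then and partly unavailable afterwards.

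**What to change.** 1. **8.1 and 8.2:** State that a device stoppage or malfunction alone is not a ground for excluding or destroying data or for replacing the subject, and that readings before the failure are kept. Reconcile this with 3.4. The change concerns data and analysis only and leaves the conduct of the operation untouched.
2. **12.4.1:** Name the samples that count as open-bowel. Report detection over all attempted subjects and samples, counting a reading missing because of the device as not detected, and show the rate among valid readings beside it. Do not enter a failed reading as zero concentration.
3. **Sample Collection Table (6.1.2):** Add one status code per sample: valid at first attempt; valid after troubleshooting; no reading, device; no reading, surgical reason. Report the counts by cohort.

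The cost is one coded field per sample, filled in by the coordinator who already operates the device, and an extra line in the results table. The stated detection rate may be slightly lower.

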**13.1.4 Reporting of AE to WCM IRB**

**This study will not be reporting AE.**

**13.1.5 Reporting Events to Participants**

**Not Applicable.**

**13.1.6 Events of Special Interest-**

**Not Applicable.**

*If applicable, include content in this section otherwise type "Not Applicable."*

**13.1.7 Reporting of Pregnancy**

**Not Applicable.**

**13.2 Definition of SAE**

SAEs include death, life threatening adverse experiences, prolongation of hospitalization, disability or incapacitation, and any other serious events that may jeopardize the subject or require medical or surgical intervention to prevent one of the outcomes listed in this definition.

**13.2.1 Reporting of SAE to IRB**

**Not Applicable.**

All SAEs occurring on this study will be reported to the IRB according to the IRB policy, which can be accessed via the following link:

[http://researchintegrity.weill.cornell.edu/forms\\_and\\_policies/forms/Immediate\\_Reportin\\_Policy.pdf](http://researchintegrity.weill.cornell.edu/forms_and_policies/forms/Immediate_Reportin_Policy.pdf).

**13.2.2 Reporting of SAE to FDA [For Protocols Where WCMC is the Sponsor-Investigator]**

**Not Applicable.**

IND application sponsor must report any suspected adverse reaction or adverse reaction to study treatment that is both serious and unexpected. Unexpected fatal or life-threatening suspected adverse reactions represent especially important safety information and must be reported to FDA as soon as possible but no later than 7 calendar days following the sponsor's initial receipt of the information.

- i. death,
- ii. a life-threatening adverse event,
- iii. in-patient hospitalization or prolongation of existing hospitalization,
- iv. a persistent or significant incapacity or substantial disruption of the ability to conduct normal life functions, or
- v. a congenital anomaly or birth defect

Important medical events that may not result in death, be life-threatening, or require hospitalization may be considered serious when, based upon appropriate medical judgment, they may jeopardize the patient or research subject and may require medical or surgical intervention to prevent one of the outcomes listed as serious

**13.2.3 Reporting of SAE to Sentire Medical Systems, Inc.**

We are reporting Unanticipated Problems/ Unexpected adverse events which include the Perf-AlertTM device stop working during surgery, or malfunction, and these events will be reported to the IRB and the device sponsor Sentire Medical Systems, Inc., USA. This is described in section 14.1.2 of the protocol, and now added to In general we are collecting intraoperative and postoperative complications.

**13.3 AE/SAE Follow Up**

**Not Applicable.**

**13.4 Time Period and Frequency for Event Assessment and Follow Up**

**Not Applicable**

**14. Unanticipated Problems Involving Risks to Subjects or Others**

**14.1 Definition of Unanticipated Problems Involving Risks to Subjects or Others (UPIRTSO)**

In this study, unanticipated adverse device effect will be defined as any unanticipated adverse device effect, any serious adverse effect on health or safety, or any life-threatening problem or death caused by, or associated with, a device, if that effect, problem, or death was not previously identified in nature, severity, or degree of incidence in the investigational plan or application (including a supplementary plan or application), or any other unanticipated serious problem associated with a device that relates to the rights, safety, or welfare of subjects (21 CFR 812.3(s)).]

#### **14.1.2 Unanticipated Problem Reporting**

The investigator will submit to the sponsor Sentire Medical Systems, Inc. and to the reviewing Institutional Review Board (IRB) a report of any unanticipated adverse device effect occurring during an investigation as soon as possible, but in no event later than 10 working days after the investigator first learns of the effect (21 CFR 812.150(a)(1)). A sponsor who conducts an evaluation of an unanticipated adverse device effect under 812.46(b) shall report the results of such evaluation to the Food and Drug Administration (FDA) and to all reviewing IRB's and participating investigators within 10 working days after the sponsor first receives notice of the effect. Thereafter the sponsor shall submit such additional reports concerning the effect as FDA requests (21 CFR 812.150(b) (1)).

### **15. Data and Safety Monitoring Plan (DSMP)**

To ensure the safety of clinical research subjects and protect the validity and integrity of research data, subjects will be well acquainted with the research study prior to signing research informed consent. Further, the subjects will be selected strictly according to the study inclusion and exclusion criteria. The electronic data collected as part of this study will be stored in a password-protected computer, and the paper data will be locked in the locked cabinet in the clinical research office located at K802C. We do not anticipate any adverse events related to this study. However, all intraoperative surgical complications will be collected as part of this study data. We will report unanticipated adverse events to the WCMC IRB and to Sentire Medical Systems.

